#### Specific Aims:

**Specific Aim 1: Determine whether a 7-week course of daily brivaracetam reduces below-level neuropathic pain in SCI.** The objective of this aim is to assess efficacy of a 7-week course of brivaracetam to reduce neuropathic pain in men and women with SCI. We will assess change in pain intensity and related outcomes, including mood, satisfaction with life, and community integration. We will monitor drug adverse events and tolerability.

**Specific Aim 2: Determine whether a 7-week course of daily brivaracetam increases parietal operculum brain connectivity.** The objective of this exploratory aim is to assess the effect of a 7-week course of brivaracetam treatment on parietal operculum activation and connectivity in SCI. We will assess changes in cortical activity of related pain perception regions and networks in the brain in response to brivaracetam treatment compared to placebo using rsfMRI and pain-related task-based fMRI. To achieve this aim, we will test the working hypothesis that brivaracetam increases parietal operculum activation and connectivity compared to placebo, using rsfMRI, task-based fMRI, and a validated image processing protocol. We will also examine changes in network connectivity and brain activity in the insula, because of its concurrent reported importance for neuropathic pain in SCI. We will assess the association between functional connectivity of the parietal operculum and the insula and change in pain intensity in response to brivaracetam treatment.

**Specific Aim 3: Determine whether baseline microRNA-485 levels are associated with response to brivaracetam treatment.** The objective of this exploratory aim is to assess microRNA expression as a potential predictive biomarker of response to brivaracetam treatment. To achieve this, we will test the working hypothesis that baseline circulating miR-485 levels predict change in pain intensity in response to brivaracetam treatment. To test this, we will use Next-Generation sequencing. We will assess miR-485 levels at baseline and after a three-month treatment course.

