For Aim 3, we will analyze miRNA expression profiles for raw cycle threshold (Ct) values using real-time Statminer software (Integromics, Inc) to identify significantly altered miRNAs. For relative quantification of miRNAs between placebo and brivaracetam-treated samples, the following steps will be performed in the Statminer software suite: quality control of biological replicates, filtering of miRNAs expression having Ct values below cycles and the detection of expression in all biological replicates of calibrator and target. Statistically significant miRNAs will be selected based on stringent parameters such as Benjamin-Hochberg FDR and data will be conservatively selected with adjusted p-values and p-value lower than 0.01 and 0.05, respectively. Functional pathway analysis of altered miRNAs and their association with genes related to reduction in neuropathic pain will be performed using Ingenuity Pathway Analysis (IPA) program (Ingenuity Systems Inc., Redwood City, CA). For clinical correlation analysis, data comparing changes in miRNA expression will be described as means with standard error of the mean. To analyze the differences between group means we will use analysis of variance after assessing for distribution and variance. We will use Games-Howell test for multiple comparisons.

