### 15.3 Statistical Analysis:

All statistical analyses will be conducted with Stata v. 17.0 or SAS v.9.4.72 assuming a 5% level of significance unless otherwise stated. Participant characteristics will be described using frequency counts and percentages (nominal variables) and means/standard deviations (SDs) or medians and interquartile ranges (IQRs) (continuous variables). Chi-square tests and t-tests or rank-sum tests will be used to compare the subject characteristics between the treatment arms.

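### Aim 3 names one hypothesis, that baseline miR-485 predicts change in pain, but the only miRNA decision rule in Section 15.1 is a between-arm panel screen that does not test it

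*Combined protocol and SAP*

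**What the plan says.** Under Specific Aims (Section 1.0), Aim 3 is labelled exploratory: "The objective of this exploratory aim is to assess microRNA expression as a potential predictive biomarker of response to brivaracetam treatment". It carries one working hypothesis about one marker: "we will test the working hypothesis that baseline circulating miR-485 levels predict change in pain intensity in response to brivaracetam treatment". Section 2.3 adds a direction: lower circulating miR-485 is expected to go with a poorer response.

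The Aim 3 paragraph of Section 15.1 describes something else. Expression profiles are analysed "to identify significantly altered miRNAs", and the steps listed are introduced by "For relative quantification of miRNAs between placebo and brivaracetam-treated samples". The selection rule is "Statistically significant miRNAs will be selected based on stringent parameters such as Benjamin-Hochberg FDR". The numerical limits are given next, in the same sentence of the plan: "data will be conservatively selected with adjusted p-values and p-value lower than 0.01 and 0.05, respectively". For clinical correlation, the paragraph describes changes in miRNA expression by means and standard errors and compares group means by analysis of variance with the Games-Howell procedure. It does not mention miR-485.

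Section 15.3 sets the general level, "assuming a 5% level of significance unless otherwise stated". Section 15.2 says that 20 per arm suffices for Aims 2 and 3, but gives no effect size, panel size or power for Aim 3.

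**The concern.** The hypothesis and the analysis do not meet. The hypothesis relates a baseline level to a later change in pain. The screen asks which miRNAs differ between placebo and brivaracetam samples. An analyst who follows Section 15.1 to the letter has two options: leave the hypothesis untested, or apply the one miRNA significance rule on the page and treat miR-485 as a member of the panel at an adjusted level of 0.01. A third option, a separate test devised at analysis, would leave model and level to be chosen after the data are seen.

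At stake is the one marker that the trial set out to examine. Section 2.2 says the results will be used to design larger trials, so a negative finding produced by a panel-wide correction, or a positive one from an analysis chosen late, could misdirect them.

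The pair of thresholds also looks odd. Two limits are stated, but only one can have any effect.

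**Working it through.** **1. The two thresholds.** With m ordered raw p-values, the BH-adjusted value is

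adjusted p(i) = minimum over j ≥ i of m × p(j) / j, capped at 1.

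Since m/j ≥ 1 and p(j) ≥ p(i), the adjusted value is never below p(i). Adjusted p < 0.01 therefore forces raw p < 0.01, and raw p < 0.05 adds nothing. A simulation of 2,000 panels of 1 to 799 markers agrees: of 188,970 markers with adjusted p < 0.01, none had raw p ≥ 0.05, and the largest raw p was 0.0095. No selection changes when the 0.05 limit is removed.

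**2. Hypothesis and analysis side by side.**

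| | Aim 3 hypothesis (Specific Aims) | Rule in Section 15.1 |
|---|---|---|
| Marker | miR-485 | all profiled miRNAs |
| Time | baseline | placebo and brivaracetam samples; time not tied to baseline |
| Question | prediction of change in pain | difference in expression between arms |
| Test and level | none given | adjusted p < 0.01 |

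The analysis of variance on group means does not fill the left-hand column, as it contains no term for baseline miR-485 as a predictor of pain change.

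**3. What the panel rule would cost miR-485.** The documents give no Aim 3 power figure to reproduce. From the documents: 20 per arm (Section 15.2), default level 0.05 (Section 15.3), adjusted level 0.01 (Section 15.1). Assumed: correlation r = 0.6 between baseline miR-485 and pain change in the treated arm, all 20 treated participants giving blood, m = 100 to 1,000 miRNAs, and no other altered marker. Under that last assumption miR-485 needs a raw p below about 0.01/m.

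Fisher z: power = Φ(atanh(r) × √(n − 3) − z(1 − α/2)).

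atanh(0.6) × √17 = 0.693 × 4.123 = 2.858.

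| Rule | α | z | Power |
|---|---|---|---|
| Alone, two-sided 5% | 0.05 | 1.960 | Φ(0.898) = 82% |
| Panel, m = 100 | 0.0001 | 3.891 | Φ(−1.033) = 15% |
| Panel, m = 1,000 | 0.00001 | 4.417 | Φ(−1.559) = 6% |

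**4. How far this depends on the assumptions.**

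- *Larger effect.* For r = 0.8, atanh(0.8) × √17 = 1.099 × 4.123 = 4.530. Power is Φ(2.570) = 99% alone, Φ(0.639) = 74% at m = 100 and Φ(0.113) = 54% at m = 1,000.
- *Other markers altered.* BH is less strict when more markers carry signal. This was simulated for a between-arm difference with 20 per arm and m = 200 to 800. An effect with 80% power alone kept about 7% to 20% when 5% to 20% of the panel was equally altered, and about 33% when half was. A 1.2 SD effect (96% alone) kept 51% to 63% when 10% to 20% of the panel was altered.
- *Fewer samples.* The biomarker draw is optional and remote participants give none (Section 5.0), so 20 treated participants is an upper figure if 20 per arm complete.

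**5. The interaction is harder to detect.** The 82% is for association within the treated arm. If r = 0.6 under brivaracetam and 0 under placebo, with 20 each, comparing the two Fisher z values gives 0.693 / √(2/17) = 2.021, and power Φ(2.021 − 1.960) = 52%. The estimate and its interval therefore matter more than the p-value.

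**The case against.** The strongest reply is that no section says miR-485 is decided by the screen. A reader might infer that it is, because no other miRNA rule is given, but Section 15.1 confines the rule to finding altered miRNAs between arms. The general 5% level in Section 15.3 could then cover a separate miR-485 test. This stands: the power loss is conditional, and the documents do not support saying that the plan makes a real miR-485 signal almost sure to fail. But a default level is not a test, and no model for the named hypothesis is written down.

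A reader might also take the two limits as alternatives, so that raw p < 0.05 would be enough and 5 to 50 false miRNAs would be expected for panels of 100 to 1,000 (0.05 × m). The text does not support this. It joins the limits as both required, in a stated order, and describes the selection as stringent and conservative. On that reading the redundancy is only a drafting flaw.

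Finally, Aim 3 is exploratory within a pilot, and a strict false discovery rate is a defensible choice for a discovery screen. That also stands, and it limits the weight of the point. It does not explain why the one pre-specified marker has no analysis of its own.

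**Conclusion.** The point holds in this form: Aim 3 has one named hypothesis, and Section 15.1 gives it no test. Its only miRNA decision rule is a between-arm panel screen that does not address baseline prediction. The raw 0.05 condition is redundant without consequence.

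If miR-485 were judged by the panel rule, power would fall from about 82% to about 15% at 100 miRNAs and 6% at 1,000, for a correlation of 0.6 in 20 treated participants with no other altered marker. Effect size, panel size and share of altered markers are assumptions, and the loss shrinks as effects grow or more markers are altered. The mismatch between hypothesis and analysis rests on the text alone and needs none of these assumptions. The change is worth making, but the primary analysis is not affected.

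**What to change.** In the Aim 3 paragraph of Section 15.1:

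- Test miR-485 alone and first, outside the screen, at two-sided 5%. Regress change in pain on baseline miR-485, treatment and a treatment-by-miR-485 term, state in advance that the interaction is the coefficient tested, and report the estimate with its 95% confidence interval.
- For all other miRNAs, keep a single BH-adjusted threshold, label the screen hypothesis-generating, and delete the raw p < 0.05 condition.

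The cost is a few sentences and one extra model. Samples, assays and visits are unchanged. The interaction will be estimated imprecisely at this sample size, which is a reason to lead with the interval when the result is reported.

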### 15.2 Power Analysis:

We present power and sample size analysis for the primary endpoint; a 2-point improvement in neuropathic pain intensity as assessed by the

International Spinal Cord Injury Pain Basic Dataset. We based our sample size calculation on variations in pain intensity observed in an ongoing clinical trial (DoD W81XWH-14-SCIRP-CTA, [name] PI). In this sample, average neuropathic pain intensity in 28 adults with SCI was  $3.43 \pm 3.17$ . Based on this, a sample size of 20 per arm will have more than 80% power to detect a significant difference in pre-post changes of neurological pain between the two arms at a two-sided significance  $\alpha$  level of 0.05. This sample size is sufficient to address the exploratory analyses proposed in Aims 2-3.

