**Resting State Brain Functional Connectivity and Neuropathic Pain.** In our ongoing SCI studies, we observe that participants display a wide range of pain levels. As hypothesis-generating preliminary data for this pilot study, we evaluated how variations in neuropathic pain levels impact resting state functional connectivity after SCI. We studied 29 participants with chronic SCI (level C6 or lower) and 11 healthy control participants using 3T MR imaging. A high resolution structural (MPRAGE) dataset and two sets of 6-minute resting state EPI datasets (TR 3 sec) were collected in each participant. Prior to the neuroimaging session, participants rated their current pain levels on a 0 to 10 VAS scale. MRI data was analyzed using the SPM12 based Conn toolbox [Whitfield-Gabrieli and Nieto-Castanon, 2012] (Version 17f, Matlab R2018b). Preprocessing steps included realignment and unwarping, slice-timing correction, ART based identification of outlier scans for scrubbing, segmentation and normalization to MNI space, and 8 mm smoothing. Denoising steps included scrubbing, aCompCor, ICA-based denoising, Global Regression, and 0.008 to 0.09 Hz band-pass filtering. Two main comparisons were evaluated: SCI participants versus uninjured controls, and the effect of concurrent pain ratings on rsfMRI measures. First, we evaluated region-of-interest (ROI) based functional connectivity in a set of anatomically defined regions known to be impacted in SCI and neuropathic pain: the periaqueductal gray, the bilateral thalamus, the amygdala, the hippocampus, the insula, anterior cingulate, the precentral and the post-central gyrus. Second, we evaluated, on a voxel-by-voxel basis, amplitude of low frequency fluctuations (ALFF) and intrinsic resting state functional connectivity. ALFF measures the total power of the BOLD signal within the low-frequency range between 0.01 and 0.1 Hz and is a measure of intensity of low frequency oscillations. Intrinsic resting state connectivity is a measure of how connected a voxel is to other voxels but does not provide information on the regions with which this voxel is connected.

SCI participants reported an average VAS pain of 3.0 ( $\pm 2.5$ ), ranging from 0 to 8, while uninjured control participants reported an average of 0.26 ( $\pm 0.64$ ), ranging from 0 to 2. The difference in pain ratings was significant ( $p=0.00053$ ).

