*International Spinal Cord Injury Pain Data Set.* This tool assesses average pain intensity in the last week using a 0-10 numerical rating scale. The 0-10 numerical rating scale has been recommended by the IMMPACT consensus group for use in pain clinical trials [Dworkin et al., 2005] and by the 2006 NIDRR SCI Pain outcome measures consensus group. [Bryce et al., 2007] This scale is recommended to standardize pain outcomes across studies. The International Spinal Cord Injury Pain Data Set also assesses dimensions of pain (i.e., intensity of pain, time of day, location, occurrence, etc.), and pain interference with mood, activity, and sleep.

*Modified Brief Pain Inventory (BPI).* The BPI is a short self-assessment questionnaire that provides information on various dimensions of pain including how pain developed, the types of pain a patient experiences, and time of day pain is experienced, as well as current ways of alleviating pain [Cleeland and Ryan, 1994]. The BPI also consists of the numeric pain rating scale, a simple 10-point scale (0 = “no pain”, 10 = “pain as bad as you can imagine”) measuring a patient’s worst pain and least pain, on average in the last 24h and at present time. The Brief Pain Inventory provides information on the intensity of pain (the sensory dimension) as well as the degree to which pain interferes with function (the reactive dimension). According to several previous studies on pain in spinal cord injury, the BPI is an effective measure [Bryce et al., 2007].

*DN4 Assessment Tool.* This is a 4-item assessment that characterizes neuropathic pain.

*Assessment of Mood with the Patient Health Questionnaire (PHQ-9).* This is a 9-item scale that assesses patient quality of life through mental state. It identifies active suicidality [Kroenke et al., 2001]. It assists physicians in both diagnosing depression and determining a treatment route. It incorporates DSM-IV depression classifications and determines severity of depression [Bombardier et al., 2004; Graves and Bombardier, 2008; Kalpakjian et al., 2009; Krause et al., 2010].

*Satisfaction with Life Scale (SWLS).* This is a 5-item scale that assesses patient happiness with current quality of life [Diener et al., 1985]. It consists of a 1-7 Likert scale.

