## 8.0 Study Population

Inclusion Criteria:

- 18 years of age or older
- Injured for  $\geq 3$  months
- Completed inpatient rehabilitation and living in the community
- Chronic sublesional neuropathic pain defined as persistent pain (VAS grade 3-10) for three months or more
- For people of child-bearing potential: currently practicing an effective form of two types of birth control (defined as those, alone or in combination, that result in a low failure rate (i.e., less than 1% per year) when used consistently and correctly).

Exclusion Criteria:

- Progressive myelopathy secondary to posttraumatic cord tethering or syringomyelia
- Active use of drugs known to interact with brivaracetam: rifampin, carbamazepine, sodium oxybate, buprenorphine, propoxyphene, levetiracetam, and phenytoin.
- Brain injury or cognitive impairment limiting the ability to follow directions or provide informed consent
- Pregnancy or lactation
- Epilepsy or active treatment for seizure disorder
- Past or current suicidality
- Active treatment for psychiatric disease
- Drug addiction
- Moderate or heavy alcohol intake (up to four alcoholic drinks for men and three for women in any single day, and a maximum of 14 drinks for men and 7 drinks for women per week)

- Hepatic cirrhosis, Child-Pugh grades A, B, and C
- Impaired renal function (GFR<60ml/minute)
- Contraindications to brivaracetam or pyrrolidine derivatives including allergy
- Active clinically significant disease (e.g., renal, hepatic, neurological, cardiovascular, pulmonary, endocrine, psychiatric, hematologic, urologic, or other acute or chronic illness) that, in the opinion of the investigator, would make the patient an unsuitable candidate for this trial.
- History of malabsorption or other gastrointestinal (GI) disease that may significantly alter the absorption of brivaracetam
- Use of any investigational drug 30 days prior to enrollment in this study
- Dependent on mechanical ventilation.
- Use a gastrostomy tube (G-Tube) for feeding.
- Enrollment in another clinical trial.

People with contraindications to MRI including retained bullet fragments, noncompatible metal implants, and implanted devices such as non-MRI compatible baclofen pumps may still be eligible for the study; they will not participate in the MRI scans.

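### The sample-size figures (pain 3.43 ± 3.17) come from a sample that cannot meet the pain 3-10 entry rule, and the stated power of more than 80% does not follow from them

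*Combined protocol and SAP*

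**What the plan says.** Section 15.2 (Power Analysis) sets the target as "a 2-point improvement in neuropathic pain intensity as assessed by the" International SCI pain dataset. On the source of the variability it says: "We based our sample size calculation on variations in pain intensity observed in an ongoing clinical trial". In that trial "average neuropathic pain intensity in 28 adults with SCI was" 3.43 ± 3.17. From this it concludes that "a sample size of 20 per arm will have more than 80% power to detect a significant difference in pre-post changes" "between the two arms at a two-sided significance" level of 0.05. It gives no SD of change and no pre-post correlation. It does not say that the 28 were selected for pain, or whether 3.43 is a baseline value.

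Section 8.0 (Inclusion Criteria) requires "Chronic sublesional neuropathic pain defined as persistent pain (VAS grade 3-10) for three months or more". Section 5.0 describes the outcome instrument: "This tool assesses average pain intensity in the last week using a 0-10 numerical rating scale".

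Nothing in the document reconciles the planning sample with the entry rule or adjusts the SD for it.

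**The concern.** A planning SD is useful only if it describes the people who will be randomised. A mean of 3.43 with an SD of 3.17 on a 0-10 scale suggests many scores at or near zero, and people with such scores are outside this trial. A person scoring below 2 also cannot improve by 2 points, so a sample with many low scores is a poor guide to how much change varies among entrants.

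The second difficulty is that 3.17 is the spread of a pain score, whereas power for a comparison of pre-post changes depends on the spread of the change. The plan does not supply the link. At stake is the only justification given for 20 per arm. Section 2.2 says the results will be used to design larger trials, so a variance estimate from the wrong people could be carried forward.

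**Working it through.** **Inputs.** From 15.2: mean m = 3.43, SD 3.17, n = 28, difference 2, 20 per arm, two-sided 0.05. From 8.0: entry range 3 to 10. From 5.0: outcome range 0 to 10. The VAS used for entry and the numerical rating scale used for the outcome are treated as the same 0-10 range. The ± is read as an SD. As a standard error it would imply an SD of 3.17 × √28 = 16.8, which is impossible on this scale.

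**1. The plan's own figure.** For a two-sample t-test with 20 per arm and a difference of 2:
- With 3.17 as the SD of change, the noncentrality is 2 / (3.17 × √(2/20)) = 2.00 and power is 49% (51% by the normal approximation). The stated figure is not reproduced.
- Power of 80% requires an SD of change of at most 2.20 (2.26 by the normal approximation).
- If 3.17 is the SD at both visits, the SD of change is 3.17 × √(2(1 − ρ)). Setting this to 2.20 gives ρ = 1 − 2.20² / (2 × 3.17²) = 0.76. The plan states no such correlation.

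**2. Can the 28 be people who meet the entry rule?** For values confined to [a, b] with mean m, the largest SD is √((m − a)(b − m)).
- On 3 to 10: √(0.43 × 6.57) = 1.68, or 1.68 × √(28/27) = 1.71 as a sample SD. The reported SD is 3.17, so this is impossible.
- On 0 to 10: √(3.43 × 6.57) = 4.75. The figures are possible for an unselected sample.

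**3. How many must have scored below 3?** On 0 to 10 the function (x − 3)(x − 10)/30 is at most 1 below 3 and at most 0 from 3 upward. Its average is therefore a lower bound on the share below 3. That average is (E[X²] − 13m + 30)/30.
- With 3.17 as a sample SD, E[X²] = 3.17² × 27/28 + 3.43² = 21.455, and the bound is (21.455 − 44.59 + 30)/30 = 0.229. Times 28 this is 6.4.
- With 3.17 as a divide-by-n SD, E[X²] = 21.814 and the bound is 0.241. Times 28 this is 6.7.

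Either way at least 7 of the 28 scored below 3, and at most 21 scored 3 or more. No distributional shape is assumed.

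**4. Illustration of power among entrants (assumptions, not plan figures).** Assume an entry SD of 2.27, which is the SD of the part at or above 3 in a rounded, clipped normal matched to 3.43 and 3.17. Assume an unselected SD of 3.17 at both visits, selection at baseline only, and linear regression of follow-up on baseline. With ρ the correlation before selection, the variance of change is (1 − ρ)² × 2.27² + 3.17² × (1 − ρ²).

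| ρ | SD of change, entrants | Power, entrants | Power, unselected |
|---|---|---|---|
| 0.3 | √11.67 = 3.42 | 44% | 38% |
| 0.5 | √8.83 = 2.97 | 55% | 49% |
| 0.7 | √5.59 = 2.36 | 74% | 71% |

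Under a different assumption, a clipped-normal model with selection at baseline, power goes from 38% to 42%, from 50% to 49%, and from 73% to 67% at correlations of about 0.32, 0.51 and 0.72. The shift is a few points and its sign changes.

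**The case against.** The strongest reply is that the population mismatch hardly moves power. In the illustrations it shifts power by a few points in either direction, and the larger gap is the missing SD of change. That stands. It is why the point covers both the wrong sample and the missing quantity, and why no direction is claimed for the mismatch.

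Other parts of the reply also stand:
- Only the pair of mean 3.43 and SD 3.17 is impossible under the entry rule. An SD of 3.17 alone is possible on 3 to 10 if the mean is between about 4.9 and 8.1.
- A two-sample comparison of changes does not use the mean, so the low starting level does not itself enter the power formula.
- 15.2 does not say that 3.43 is a baseline value. If it were a later value, it would still not describe people at entry.
- Entry and outcome use differently named scales, so an occasional entrant could be rated below 3. That does not plausibly account for a quarter of a sample.
- The imaging sample in section 2.2, where "SCI participants reported an average VAS pain of 3.0" (range 0 to 8), was rated on current pain and is not used for planning. It is context only.
- A baseline-adjusted analysis would need a correlation of about 0.72 rather than 0.76. Section 15.1 does not name baseline pain as a covariate, and 15.2 does not mention such an analysis.

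Three stronger readings are tempting and are not supported. A reader might infer that the trial is underpowered; the documents do not give the SD of change, so this is not shown. A reader might infer that entrants vary less, so the stated power is conservative; a narrower baseline range can also lower the pre-post correlation. And a reader might apply the narrower entry SD at both visits, which would give more favourable figures; the rule applies at entry only, and follow-up scores can fall anywhere from 0 to 10.

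**Conclusion.** The point holds. The sample behind the power statement cannot be one of people who meet the entry rule: at least 7 of its 28 members scored below 3. This is arithmetic on the plan's own figures and rests only on reading both scales as 0-10 and the ± as an SD.

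The stated power also does not follow from the stated figures. It is about 49% if 3.17 is the SD of change. It exceeds 80% only if that SD is below about 2.2, or if the correlation is above about 0.76 with 3.17 at both visits. The true power for eligible participants is unknown. The 44%, 55% and 74% illustrate how widely it can vary under stated assumptions and are not estimates for this trial.

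**What to change.** In 15.2, replace 3.43 ± 3.17 as the basis of the calculation with an SD of pre-post change for people rated 3 or more at baseline, leaving follow-up scores untruncated. In order of preference:
- take it from the cited trial, if pre-post data from it are available to the team;
- otherwise use the blinded pooled SD of change from participants already enrolled here;
- otherwise state an assumed range with its reasons.

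Name the source, the analysis assumed and any correlation used. Restate power with 20 per arm as the range that results, and write the target as a 2-point between-arm difference in mean change.

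The cost is a re-tabulation or a short recalculation and an amended paragraph; no extra patients are required. The restated power may be less favourable. An SD from at most 21 people will be imprecise, which is a further reason to report a range. The blinded pooled SD also absorbs any treatment effect: with equal arms and a true 2-point difference it adds (2/2)² = 1 to the variance.

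### The stated power of more than 80% with 20 per arm does not follow from the inputs in Section 15.2, which give no SD of pre-post change

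*Combined protocol and SAP*

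**What the plan says.** Section 15.2 (Power Analysis) sets the target as "a 2-point improvement in neuropathic pain intensity as assessed by the" International SCI Pain Basic Dataset. For variability it says: "We based our sample size calculation on variations in pain intensity observed in an ongoing clinical trial". The figure follows: "average neuropathic pain intensity in 28 adults with SCI was" 3.43 ± 3.17. On that stated basis it concludes that "a sample size of 20 per arm will have more than 80% power to detect a significant difference in pre-post changes of neurological pain", and the contrast is "between the two arms at a two-sided significance" level of 0.05. Section 15.3 also works at 5% ("assuming a 5% level of significance unless otherwise stated"). Section 15.2 then calls the same sample size sufficient for the exploratory Aims 2 and 3.

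Three other sections bear on the claim:

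- Section 15.1 makes the first analysis an unadjusted t-test with unequal variances (alongside a rank-sum test). A regression follows, whose example covariates are demographics, severity and time since injury. Baseline pain is not named.
- Section 8.0 admits only people with "Chronic sublesional neuropathic pain defined as persistent pain (VAS grade 3-10) for three months or more".
- Section 10.0 plans to enrol up to 48, expects 20% attrition and anticipates 40 completers.

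**The concern.** A comparison of pre-post changes depends on the SD of the change. Section 15.2 quotes the SD of pain intensity at one time. The two coincide only if the pre-post correlation is 0.5 and the SD is the same at both times. The plan states no correlation, no SD of change and no formula. If the quoted SD is put straight into the stated comparison, power comes out far below 80%.

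This is the only quantitative justification of the sample size for the primary endpoint. Section 2.2 says the results will be used to design larger trials. A null result would be read as coming from a trial with more than 80% power for a 2-point effect, and the plan does not support that reading.

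**Working it through.** **Inputs.** Difference δ = 2 points, read as the between-arm difference in change because that is the contrast tested; n = 20 per arm; two-sided α = 0.05; SD = 3.17 (all Section 15.2). Allocation is 1:1 (Section 5.0). The test is a two-sample t-test (Section 15.1).

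**Step 1: try to reproduce the plan's figure.** Use 3.17 as the SD of the analysed variable.

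- Standardised difference: 2 / 3.17 = 0.631.
- Standard error: 3.17 × √(2/20) = 1.002.
- Noncentrality: 2 / 1.002 = 1.995, against a critical t of 2.024 on 38 df.
- Power: **49.4%** (51.4% by normal approximation).

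Variants of the two-arm comparison also fall short:

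| Variant (SD 3.17) | Power, t-test |
|---|---|
| 20 per arm, two-sided | 49% |
| 20 per arm, one-sided | 62% |
| 24 per arm (all 48 enrolled, no loss) | 57% |
| 19 per arm (48 × 0.8 = 38.4 completers) | 47% |

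With SD 3.17 and 20 per arm, the difference detectable at 80% power is 2.88 points. The stated figure of more than 80% is not reproduced.

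**Step 2: treat 3.17 as the SD at each time point.** For an unadjusted change score, SD of change = 3.17 × √(2(1 − ρ)), where ρ is the pre-post correlation.

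| ρ (assumed) | SD of change | Power, t-test |
|---|---|---|
| 0.3 | 3.75 | 38% |
| 0.5 | 3.17 | 49% |
| 0.6 | 2.84 | 58% |
| 0.7 | 2.46 | 71% |
| 0.76 | 2.20 | 80% |
| 0.8 | 2.00 | 87% |

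**Step 3: find what 80% requires.** Solving the t-test power for the SD gives 2.20. The correlation that produces it is ρ = 1 − (2.20/3.17)²/2 = 0.76. With adjustment for baseline, the residual SD is 3.17 × √(1 − ρ²), so ρ = √(1 − (2.20/3.17)²) = 0.72. None of these values appears in the plan.

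**Step 4: allow for the entry floor.** A mean of 3.43 with SD 3.17 on a 0-10 scale suggests that the source sample included many people with little pain. The trial requires 3-10. The spreads below are illustrative assumptions, each taken with ρ = 0.5 so that the SD of change equals the SD shown:

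| Assumed spread over 3-10 | SD | Power, t-test |
|---|---|---|
| Uniform on the eight whole scores 3 to 10 | 2.29 | 77% |
| Continuous uniform, 7/√12 | 2.02 | 86% |
| Normal (3.43, 3.17) truncated to 3-10 | 1.72 | 95% |

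Power therefore depends on quantities that Section 15.2 does not give, and it can lie on either side of 80%.

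**The case against.** The strongest defence is that 3.17 was never the SD of change, so a calculation that uses it as such cannot refute the claim. A correlation of 0.5 is as much an assumption as any other. The trial's population is also narrower than the source sample, and two of the three restricted-range scenarios above exceed 80%. Adjustment for baseline, which the open covariate list in Section 15.1 does not rule out, would lower the correlation needed to about 0.72; at 0.7 it gives 78%. The claim may therefore be true.

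All of this stands, and it limits the conclusion. A reader might infer that the trial's power is 49%, or that it will miss a true 2-point effect half the time. The documents do not support that, because no document reports an SD of change of 3.17. But the defence does not rescue the sentence in Section 15.2. That sentence rests the claim on the quoted figure alone and makes no argument from correlation, range restriction or baseline adjustment.

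A reader might also infer how the figure arose, for instance that a per-arm number was taken as the total. With SD 3.17, the normal approximation gives 80.6% both for 40 per arm and for a one-sample calculation with n = 20. Since both routes give the same figure and the plan shows no formula, its origin cannot be established.

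**Conclusion.** The point holds in a conditional form. The claim of more than 80% power with 20 per arm is not derivable from the inputs that Section 15.2 gives. It needs an SD of change of about 2.2 or less. If 3.17 is the SD at each time point, that is a pre-post correlation of about 0.76 for an unadjusted change score, or about 0.72 with baseline adjustment. If the SD of change were 3.17, power would be about 49%.

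These figures assume a two-sample t-test at two-sided 5%, 20 evaluable per arm, and 2 points as the between-arm difference in change. The failure to reproduce the claim is firm. The trial's actual power is unknown.

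**What to change.** In Section 15.2, replace the power sentence with one that states the SD of change, its source and the test assumed, and recompute the power from these. The preferred source is the cited ongoing trial, restricted to participants with baseline pain of 3 or more, because that matches the entry criterion in Section 8.0. If the calculation relies on baseline adjustment, give the correlation and name baseline pain as a covariate in Section 15.1.

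If that SD is not available, withdraw the claim of more than 80% and give power over a range labelled as assumptions. For example: about 38%, 49%, 71% and 80% for an SD of change of 3.75, 3.17, 2.46 and 2.20, with 20 evaluable per arm and a 2-point difference. An SD of change of 3.17 should not be written in as if it had been observed.

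The cost is one paragraph and no additional participants. The downside is that the stated power may become less favourable.
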